2.1 STUDY RATIONALE

Short pre-surgical trials (also known as “window” trials) are non-therapeutic studies in which patients are treated for 2 to 3 weeks immediately after their diagnostic biopsy and before breast surgery (1). Biomarkers of cellular activity (Ki67) and/or drug target modulation are measured in intraoperative biopsies and/or the surgical specimen. Because these studies do not have a therapeutic intent, patient safety and reasonable knowledge of the optimal drug dose are major considerations for this approach so delays and/or complications from surgery are avoided. In a review of “window” trials in >4,000 patients and in all breast tumor types, there were only two deaths related to investigational drugs, and only 1% of patients could not undergo surgery due to adverse events (1, 2).

These short-term preoperative ‘window’ studies are a validated strategy to provide rapid and cost-efficient proof-of-concept for novel treatment approaches by assessing the direct effects of the study treatment on the tumor tissue (1, 2). The principle is to have access to tumor tissue before, under and after treatment for pharmacodynamic assessment and correlative studies thus providing critical insight into the optimal patient population, differences in activity between agents, influence of the tumor biology on sensitivity, and molecular mechanisms of response or resistance.

Detailed studies in the neoadjuvant setting in prospective randomized clinical trials have demonstrated the utility and validity of changes in Ki67 as a predictor of benefit from treatment and of long-term outcome (3, 4). In the neoadjuvant IMPACT study, suppression of Ki67 at 2 weeks was greater with anastrozole than with either tamoxifen or the combination of anastrozole plus tamoxifen, and this correlated with recurrence-free survival (5, 6).

Although Ki67 measurements in preoperative trials cannot replace the need for adjuvant trials with clinical endpoints, they can be highly instructive in selecting or rejecting candidate approaches for Phase III studies and defining the most appropriate patient populations.

The purpose of the proposed short-term preoperative study is to evaluate the pharmacodynamic activity of two doses of amcenestant, a potent, orally bioavailable, and selective ER inhibitor that belongs to the SERD class of compounds in comparison with letrozole. Amcenestant antagonizes the binding of estradiol to ER and promotes the transition of ER to an inactive conformation that leads to up to 98% receptor degradation at nanomolar concentrations in cellular assays. These dual properties of amcenestant translate in a deeper inhibition of ER pathways and a more effective anti-proliferative activity in ER-dependent breast cancer cell lines driven by mutant or wild type ER compared to fulvestrant.

2.2 BACKGROUND

Breast cancer is the most commonly diagnosed cancer and the second leading cause of death in women (7). In the United States (US) in 2019, it was estimated 268,600 new cases of invasive breast cancer as well as 62,930 additional cases of in situ breast cancer would be reported. Approximately 41,760 women were expected to die from breast cancer in 2019 (8).

Based on data from 2008 to 2014, the 5-year relative survival of individuals with breast cancer of all stages is 89.9% (9). Although the survival of patients with early breast cancer (defined as cancers that may have spread to nearby lymph nodes but not to distant parts of the body, ie, Stages I, IIA, IIB, and IIIA) is favorable, the survival of patients with advanced metastatic breast cancer (mBC) is poor; the 5-year relative survival is 100% for Stage I, 93% for Stage II, 72% for Stage III, and 22% for Stage IV (10, 11). Both endogenous and exogenous steroid hormones such as estrogen and progesterone have been implicated in the pathogenesis of breast cancer. Clinical treatment decisions are driven by the expression of estrogen receptors (ERs), progesterone receptors and human epidermal growth factor receptor (HER2) receptor status into HER2+, ER+/HER2- and triple negative clinical subtypes. About 75% of breast cancers express estrogen receptor alpha (ER α) which is a hormone regulator transcription factor (12). ER-positive breast cancers respond well to therapy targeting ER signaling either through competitive binding of ER antagonists such as tamoxifen or by blocking the production of estrogen by aromatase inhibitors (AIs) (13).

2.3 BENEFIT/RISK ASSESSMENT

This study has no direct benefit to the breast cancer patient who is indicated for an immediate surgery with no need of neoadjuvant therapy. The aim of the study is to assess the magnitude of Ki67 decrease with amcenestant compared to letrozole together with some other biomarkers that could be of importance for increasing our understanding of breast cancer, the selection of adjuvant therapy and potential targeted therapy in case of recurrence of the disease. More detailed information about the known and expected benefits and risks and reasonably expected adverse events (AEs) of amcenestant may be found in the Investigator's Brochure.

3 OBJECTIVES AND ENDPOINTS

Table 1 - Objectives and endpoints

Objectives	Endpoints
Primary	
To determine whether amcenestant given at 2 different doses improves the antiproliferative activity when compared to letrozole.	Change in Ki67 (percentage of positive tumor cells tested by immunohistochemistry [IHC]) after a 14-day treatment period compared to baseline assessed by central reading.
Secondary	
To assess the proportion of participants with a relative decrease from baseline in Ki67 $\geq 50\%$ in the three treatment arms.	The proportion of participants with relative decrease from baseline in the proliferation marker Ki67 (% positive tumor cells) $\geq 50\%$ as tested by IHC after a 14-day treatment period compared to baseline.
To assess ER degradation in biopsies in participants in the three treatment arms.	Change in ER expression measured by H-Score after a 14-day treatment period compared to baseline.
To assess safety in the three treatment arms.	AEs/SAEs and laboratory abnormalities.
Tertiary/exploratory	
To assess the pharmacokinetics (PK) of amcenestant 400 mg QD and 200 mg QD.	Amcenestant plasma concentrations.
To assess the complete cell cycle arrest (CCCA: Ki67 $\leq 2.7\%$) rate in the three treatment arms.	The proportion of participants achieving CCCA (Ki67 $\leq 2.7\%$) after a 14-day treatment period.
To determine the expression of additional tumor protein biomarkers (eg, BCL2, etc) and the RNA profile over time in the three treatment arms.	Change in protein expression (as measured by H-score) and in RNA expression profile on tissue sample after a 14-day treatment period compared to baseline.
To assess protein biomarkers in tumor tissues by using digital image-based methods and changes over time in the three treatment arms	Protein expression at baseline and change over time compared to baseline, by means of digital image-based method, after a 14-day treatment period.
To determine the DNA mutation profile in tumor and cell-free DNA (cfDNA) to assess a potential link with Ki67 effect.	DNA mutation profile in tumor on tissue sample and cfDNA in blood sample at baseline and after a 14-day treatment period, and change in cfDNA mutation profile after a 14-day treatment period compared to baseline.
To evaluate PK/PD relationship of amcenestant with pharmacodynamics and/or safety.	Amcenestant PK, biomarker expression and electrocardiogram (ECG).
To assess the Eastern Cooperative Oncology Group (ECOG) response rate in the three treatment arms.	ECOG response according to ECOG response criteria (14) (based on breast tumor shrinkage, pCR and ECOG performance status) after a 14-day treatment period.
To assess the Preoperative Endocrine Prognostic Index (PEPI) risk score of the three treatment arms.	PEPI risk score assessed after a 14-day treatment period.
To assess in participants the pathological complete response (pCR) of amcenestant given at 2 different doses and letrozole.	The proportion of participants achieving pCR after a 14-day treatment period.

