Pharmacokinetic data were obtained from two Phase 1 studies: one study in healthy post-menopausal women after a single dose of 100 to 400 mg and one study mentioned above in mBC patients after repeated QD administration from 20 to 600 mg. From a total of 16 patients dosed QD repeatedly with amcnestrant in Study TED14856, a high variability of exposures was observed after the first dose (average CV >60%) and a moderate variability after repeated administrations (average CV ~ 45%). The PK profile generally showed a rapid absorption (median time to achieve maximum concentration (t_{max}) ~ 3h) followed by a biphasic elimination profile. Overall across doses, apparent volume of distribution was large (~ 120 L), and apparent systemic clearance was low (~ 14-15 L/h). Preliminary data from the single ascending dose study in healthy population (100 to 300 mg in fasted state) showed a terminal half-life around 20 h. A moderate accumulation was observed on Day 21/22 after QD administrations up to 200 mg while no accumulation was observed at higher doses. Exposure (C_{max} , AUC_{0-24h}) increases with the dose after single dose, and up to 400 mg after repeated once daily administrations, slightly less at 600 mg. When given with food, no major increase of exposure was observed (no change on C_{max} and ~ 30 % increase on AUC_{0-24h}) with a delay on t_{max} by 1 hour.

At the time of the dose escalation analyzes, a partial response was observed in 1 patient receiving 150 mg daily, stable disease in 8 patients (50%) and progressive disease in 7 patients (43.8%). In accordance to the results obtained from these three parameters, safety, ¹⁸F-FES-PET scans and pharmacokinetics, the recommended dose of amcnestrant was fixed at 400 mg QD. This recommended dose was established in mBC patients, however for patients with early breast cancer, a lower dose of 200 mg QD is thought to be of interest and is being explored with the assumption that adjuvant therapy is usually 5 years and this will allow selection of the most optimal exposure to therapy.

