2.1.5 Pharmacokinetic variables

SAR439859 plasma concentrations will be determined at the predefined time point according to the SoA presented in Section 1.3 of the protocol.

In addition, population PK approaches might be used to calculate individual PK parameters estimates. The population PK analysis, if any, will be described in a separate report.

PK concentrations (and potentially PK parameter estimates) will be used to conduct an exploratory PK/PD relationship analysis of SAR439859 with pharmacodynamics (eg, Ki67) and/or safety (eg, triplicate ECG parameters, incidence of AEs).

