Assuming Ki67 value follows a log-normal distribution, $\log(Ki67_{post})$ and $\log(Ki67_{pre})$ will be used to denote the logs of the post-treatment and baseline values respectively. 0.1% will be added to untransformed Ki67 with 0 value to avoid the mathematical anomaly that arises because the log of zero is minus infinity. As a consequence of the assumption of a lognormal distribution, the log proportional changes ie, $\log(Ki67_{post}/Ki67_{pre})$ is also normally distributed. The log proportional change will be compared between treatment arms using an analysis of covariance (ANCOVA) model adjusting for the log Ki67 at baseline. Geometric LS-means ratio of proportional change (and associated 95% CI) between treatment arms will be calculated from the estimate (and associated 95% CI) of the difference of least squared (LS)-means of the log-proportional change (and associated 95% CI) from the ANCOVA model and converted by antilog transformations. For each treatment arm, geometric LS-means of the proportional change from baseline (and associated 95% CI) will be obtained from the ANCOVA model after conversion by antilog transformations. Geometric LS-means of percentage reduction in Ki67 (and associated 95% confidence intervals) will be calculated with 1 minus geometric LS-means of proportional change (and associated 95% confidence intervals). Hypothesis test will not be performed due to early enrollment termination.

Details of primary analysis can be found in [Appendix D](#).

Evaluation of inter-reader variability

The reproducibility of Ki67 measurements among readers will be estimated by calculating an intraclass correlation coefficient (ICC). The definition along with the statistical model for ICC estimation are provided in [Table 3](#).

Table 3 - Estimation of ICC during the trial

Notation	Definition	Model	Consistency or absolute agreement
ICC	The inter-reader agreement on log proportional change from baseline in Ki67 measurement after 14-day treatment period.	Mixed-effect model adjusted for baseline covariate, based on single rating	Absolute agreement

Mean estimations along with 95% confidence intervals will be reported for the ICC. Details of ICC estimation can be found in [Appendix E](#).

The ICC estimate will be checked at the following time-points:

- The interim analysis when 20 patients in each arm evaluable for the primary endpoint ([Section 3](#))

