2.4.9 Pharmacokinetic/Pharmacodynamic analysis

2.4.9.1 PK / PD analyses

Graphical presentation of SAR439859 PK concentrations (and possibly PK parameters of interest) will be done in regards of efficacy/PD endpoints. Efficacy/PD endpoint would include but may not be limited to Ki67 expressed as % change from baseline, change in ER expression H-Score or ER activation score (degradation). Plasma concentrations below LLOQ will be replaced by LLOQ/2.

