2.4.9.2 Concentration-ECG analyses

Exploratory plots

The relationship between change from baseline of ECG parameters and SAR439859 concentrations will be first explored graphically, in order to investigate any potential delayed or sustained effects and the type of modeling to be done, using the following plots, by treatment group:

- Plot of mean (\pm SEM) change from baseline in ECG data and mean SAR439859 concentration versus time (hours post-dose) overlaid onto the same plot.
- A scatterplot for PK plasma concentration versus change from baseline in ECG parameter, including trend lines (simple linear regression and loess line)

Concentration - ECG analyses will be performed for the QTcF, heart rate, PR and QRS intervals.

Time-matched pharmacokinetic concentrations will be used.

Modeling

In case of direct and linear relationship between concentrations and change from baseline in ECG parameters (QTcF, HR, PR, and QRS), a linear mixed effect model will be carried out, with population intercept, fixed terms for nominal time, with the concentration (slope) and the baseline ECG parameter (centered baseline values: subject's baseline minus the mean of the overall population) as covariates, and with random terms for individual subject deviation from the population intercept and slope, using SAS Proc Mixed. The analysis model was the following:

Change from Baseline in ECG parameter_{ij} = ($\alpha + A_i$) + $\gamma \times$ Baseline ECG_i + C \times Time_j + $\beta \times$ Concentration_{ij} + e_{ij}

with:

- α and β are the fixed population intercept and concentration slope.
- γ is the fixed effect for the baseline ECG slope
- A_i is the random intercept for the i^{th} subject, with A_i assumed to be normally distributed with null mean and an unstructured variance-covariance matrix per subject block.
- C is the fixed effect associated with Time_j (0 for pre-dose of D14 and 1 for 3h post-dose of D14)
- e_{ij} represents i.i.d. standard normal errors.

The estimates of each effect of the model, along with their 95% confidence interval, will be provided. In addition, prediction of change from baseline in ECG parameters at selected concentrations (geometric mean concentration at 3h of D14 for each dose) will be also calculated from the model (estimates and 90% confidence intervals). The scatter plot of individual ECG values versus PK concentrations with the regression line overlaid will be also provided.

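### For Ki67, the exposure-response plan is plots of concentration against % change only: no slope or interval, and not the log scale that the SAP uses to model Ki67

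*Protocol*

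**What the plan says.** Protocol section 3, Table 1, lists among the exploratory objectives "To evaluate PK/PD relationship of amcenestant with pharmacodynamics and/or safety". SAP 2.1.5 says that concentrations, and possibly PK parameter estimates, "will be used to conduct an exploratory PK/PD relationship analysis of SAR439859 with pharmacodynamics (eg, Ki67" being the first example given. The method is in SAP 2.4.9.1: "Graphical presentation of SAR439859 PK concentrations (and possibly PK parameters of interest) will be done in regards of efficacy/PD endpoints". On the scale, it says "Efficacy/PD endpoint would include but may not be limited to Ki67 expressed as % change from baseline". No regression, correlation, slope or interval is named for Ki67.

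Two other parts of the SAP go further.

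- **Primary analysis (2.4.5.1.1 and Appendix D).** Ki67 is assumed log-normal, and "The log proportional change will be compared between treatment arms using an analysis of covariance (ANCOVA) model adjusting for the log Ki67 at baseline".
- **Concentration-ECG (2.4.9.2).** This is the safety side of the same objective. If the relationship looks direct and linear, a mixed model with a concentration slope is fitted, and "The estimates of each effect of the model, along with their 95% confidence interval, will be provided".

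On exposure, protocol 4.3 reports "a moderate variability after repeated administrations (average CV ~ 45" percent). It also says that exposure rises with dose up to 400 mg on repeated dosing, and it justifies the 200 mg arm as a way to choose the best exposure for long adjuvant use.

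**The concern.** If Ki67 is log-normal, equal proportional effects are equal distances on the log scale but unequal distances on the % change scale. The inequality is worst near -100%, where a potent drug puts most of its patients. A plot on that scale squeezes together the participants whose suppression the trial wants to tell apart, and gives visual weight to the few poor responders.

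A plot alone also gives no effect size. A reader cannot say how much residual Ki67 changes with concentration, or how uncertain that is. This has some weight here because the second dose was added to inform the choice of exposure and, after early termination, SAP 2.4 leaves only descriptive estimates and intervals.

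**Working it through.** **Inputs.** Protocol 9.2 and SAP 1.3: geometric mean residual Ki67 15% in each amcenestrant arm and 30% in control; SD of log change 1; 40 evaluable per arm; one-sided 2.5% with Hochberg. Protocol 4.3: CV about 45% after repeated dosing. Not in the documents, so assumed: the 400 mg to 200 mg exposure ratio r (shown for 1.33 to 2) and the amcenestrant N after early termination (shown for 40 to 80).

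**1. The plan's own figure.** The PK/PD objective has none. The sample-size figure checks the inputs: with difference 0.693, SD 1 and 40 per arm, simulating Hochberg with a shared control and two-sample t-tests gives 84.7% marginal and 91.6% disjunctive power. The plan states 85% and 91.5%, so it is reproduced.

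**2. Where the data lie on the % scale.** % change = 100 × (exp(ln 0.15 + z × SD) - 1). With SD 1:

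| Percentile | % change |
|---|---|
| 10th | -95.8 |
| 25th | -92.4 |
| 50th | -85.0 |
| 75th | -70.6 |
| 90th | -46.0 |

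Half of the participants occupy the 15 points between -100% and -85%. The share below -70% is Φ(ln(0.30/0.15)/1) = 75.6% (80.7% at SD 0.8, 71.8% at SD 1.2).

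**3. What a halving looks like.** On the log scale it is always 0.693. On the % scale it is 30 points from 60% to 30%, 15 from 30% to 15%, 7.5 from 15% to 7.5%, and 3.75 from 7.5% to 3.75%.

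**4. Loss in a linear summary.** If log response and log concentration are jointly normal, correlation on the % scale is the log-scale correlation times s/√(exp(s²) - 1), where s is the log SD of the response. At s = 1 this is 1/√1.718 = 0.76, and its square, the relative efficiency, is 0.58. At s = 0.8 it is 0.71 and at s = 1.2 it is 0.45.

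**5. What a slope would deliver.** Within-dose SD of ln concentration = √ln(1 + 0.45²) = 0.429. Pooling two equal arms gives √(0.429² + (ln r/2)²) = 0.552 at r = 2 and 0.452 at r = 1.33. Slope SE = 1/(that SD × √(N - 2)). The 95% limits for the residual-Ki67 ratio per doubling are the estimate multiplied and divided by exp(t × SE × ln 2):

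| N | r = 2 | r = 1.33 |
|---|---|---|
| 80 | 1.33 | 1.41 |
| 60 | 1.39 | 1.50 |
| 40 | 1.51 | 1.65 |

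These take residual SD 1 and concentration measured without error. Adjusting for log baseline could narrow them.

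**6. Power, for scale only.** Assume a true slope of -0.5 per unit ln concentration, r = 1.5 and a two-sided 5% test. At N = 80 without concentration noise, power is about 54% on the log scale and 38% on the % scale. If half of the within-dose variance is sampling noise, it is about 23% and 16%. At N = 40 with that noise, it is about 13% and 10%.

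**The case against.** The strongest reply is that this is the lowest tier of objective and the documents leave room. The endpoint list in SAP 2.4.9.1 is open, protocol 9.4.3 allows a dedicated PK/PD SAP, and SAP 2.1.5 mentions possible population PK. That is true, so it cannot be said that no Ki67 exposure-response estimate will ever be made. But none of these commits to one, and the SAP refers to no separate PK/PD plan for Ki67.

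Other points stand in part.

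- **The % scale is the plan's own.** SAP 2.1.3.1 defines the primary endpoint as percentage reduction, and the waterfall plot shows % change. The modelling, however, is on the log scale.
- **The log scale has its own weakness.** A zero becomes 0.1% under the primary rule. From a baseline of 20%, ln(0.1/20) = -5.3, which is 3.4 SDs below the expected -1.9. A few zeros could drive a slope. This stands, and the fix must handle it.
- **The ECG contrast is soft.** That model is conditional on a direct linear relationship and has two time-matched observations per participant. Ki67 has one post-treatment value.
- **There may be no slope to find.** The design assumes the same 85% reduction at both doses, and protocol 4.3 reports 88-100% inhibition of ER binding from 150 to 600 mg. A plateau is possible. The efficiency and power comparisons assume a log-linear truth, which favours the log scale.

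A reader might go further and infer that measured concentration carries many times the information of the dose comparison, because "A moderate accumulation was observed on Day 21/22 after QD administrations up to 200 mg while no accumulation was observed at higher doses". The documents do not support that. The same section says that exposure rises with dose up to 400 mg on repeated dosing. A large gain, for example a ten-fold smaller slope variance, needs an assumed exposure ratio near 1.33 and noise-free concentrations. The CV comes from 16 patients over five doses.

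**Conclusion.** The concern holds as a modest one. For Ki67 the SAP specifies plots on the % change scale, with no slope or interval, and that scale does not match its own log-normal model. Under the design assumptions half of the amcenestrant data sit in the last 15 points of the axis. A linear summary there has about 0.58 relative efficiency (0.71 to 0.45 for log SD 0.8 to 1.2), provided the effect is log-linear.

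What is missing is an estimate, not a test. At the reduced sample size power would be low on either scale, and the interval per doubling would be wide (roughly ×/÷ 1.3 to 1.65). Exposure within a dose is not randomised, so any slope is observational. Nor does it follow that the plots are useless, since they show every participant, or that the dose question goes unanswered: the arms are still compared on the log scale with geometric LS-means, ratios and 95% CIs. The primary analysis is unaffected. Label: cheap improvement.

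**What to change.** In SAP 2.4.9.1:

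1. Keep the plots, but show log(Ki67 post/Ki67 pre), or residual Ki67 on a log axis.
2. Add one exploratory linear model over both amcenestrant arms: log proportional change on log concentration plus log baseline Ki67. Report the ratio of residual Ki67 per doubling of concentration with a 95% CI, labelled descriptive. Repeat it with dose arm in the model, to show how much rests on non-randomised variation within dose.
3. Apply the primary analysis's 0.1% rule to zero Ki67 values, and check that they do not drive the slope, for example by refitting without them.
4. First reconcile the PK sampling times. SAP 2.4.7.1 gives windows for a pre-dose sample on Day 7 and a 3 h sample on Day 15. The protocol schedule has D14 pre-dose, D14 3 h and D15 24 h after the last dose. Then name the concentration used as the exposure measure.

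If a dedicated PK/PD plan already covers this, a cross-reference is enough. The cost is a few lines of SAP text and one regression on data already collected. The one risk is over-reading an observational slope, which the label and the dose-adjusted repeat address.
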